9.6.4 Nasal Endoscopy

Nasal endoscopies (blinded centralized evaluation) will be performed at Screening, on Day -3, pre-dose on Days 21 and 49, and on Days 84 and 112 or ET for efficacy analyses. Videos of the endoscopy will be evaluated by independent blinded reviewer.

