12 DISCONTINUATION AND REPLACEMENT OF PATIENTS

12.1 Early Discontinuation of Study Drug

A patient may be discontinued from study treatment at any time if the patient, the Investigator, or the Sponsor feels that it is not in the patient's best interest to continue. The following is a list of possible reasons for study treatment discontinuation:

- Patient's withdrawal of consent
- Patient is not compliant with study procedures
- AE that, in the opinion of the Investigator, results in it being in the best interest of the patient to discontinue study treatment
- Protocol violation requiring discontinuation of study treatment
- Loss to follow-up
- Sponsor's request for ET of study
- Positive pregnancy test (females)

If a patient is withdrawn from treatment due to an AE, the patient will be followed and treated by the Investigator until the abnormal parameter or symptom has resolved or stabilized.

All patients who discontinue study treatment should come in for an ET visit as soon as possible.

All patients are free to withdraw from participation at any time for any reason, specified or unspecified, and without prejudice.

Reasonable attempts will be made by the Investigator to provide a reason for patient withdrawals. The reason for the patient's withdrawal from the study will be specified in the patient's source documents. Refer to [Table 1](#) for ET procedures.

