12.2 Withdrawal of Patients from the Study

Participation of a patient will be discontinued in the event that:

- An AE or SAE that, in the judgment of the Investigator, requires treatment withdrawal due to its nature, severity, or required treatment, regardless of the causal relationship to treatment
- Protocol violations, including non-compliance, loss to follow-up

- Occurrence of an exclusion criterion that is clinically relevant and affects the patient's safety, if discontinuation is considered necessary by the Investigator and/or Sponsor
- Serum transaminases (ALT and/or AST) $>3 \times$ upper limit of normal (ULN) AND total bilirubin $>2 \times$ ULN (confirmed by subsequent repeat) without an alternative explanation
- Elevation of ALT or AST $>3 \times$ ULN (confirmed by repeat) with the appearance or worsening of symptoms felt by the Investigator to be potentially related to hepatic inflammation, such as fatigue, nausea, vomiting, right upper quadrant pain or tenderness, fever, rash, or eosinophilia
- Use of a non-permitted concomitant drug, as defined in [Section 7.1](#)
- Withdrawal of the patient's consent
- Participation in any other trial during the duration of this trial
- Loss of ability to freely provide consent through imprisonment or involuntary incarceration for treatment of either a psychiatric or physical (e.g., infectious disease) illness
- Discretion of the Investigator

All patients are free to withdraw from participation at any time for any reason specified or unspecified, and without prejudice.

Reasonable attempts will be made by the Investigator to provide a reason for patient withdrawals. The reason for the patient's withdrawal from the study will be specified in the patient's source documents. As noted above, patients who discontinue study treatment early (i.e., they withdraw prior to Day 168) should have an ET visit. Refer to [Table 1](#) for ET procedures. Patients who withdraw after Day 84 but prior to Day 168 should be encouraged to come in for a final visit.

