12.3 Replacement of Patients

Patients who do not meet all eligibility criteria at Screening or who qualify at Screening but do not enter the Run-in period within 6 weeks may be rescreened once and assigned a new Screening number.

Patients who withdraw prematurely from the study will not be replaced.

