15.1.3 Efficacy Populations

The main population for efficacy will be the Modified Intention-to-Treat Population, defined as all patients randomized who receive at least 1 dose of study drug and have a valid Baseline measurement and at least 1 post-baseline efficacy assessment. Patients will be analyzed for efficacy according to the group to which they were randomized.

In addition, the primary efficacy analyses will also be performed for the Per-Protocol Population, defined as patients who have a Week 12 visit and valid efficacy measurements.

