15.3 Analysis of Primary Endpoint

The effect of 2 different dose levels of AK001 in combination with an INS versus the INS alone on the reduction in size of nasal polyps as evaluated by the change from Baseline to

Week 12 after the start of treatment in TPS (Appendix 2 [Section 19.2](#)) will be displayed for each treatment group by study visit using summary statistics, including the number of observations, the mean, median, standard deviation (SD), and range. Each active treatment group will be compared separately with the placebo group for change from Baseline in TPS by using a mixed effect repeated measures analysis of variance (ANOVA) model with specific contrast statement for Week 12 and for each comparison separately. Adjustment in alpha for multiple comparisons will be controlled according to the Hochberg method, in which, if the efficacy comparison of the high active arm versus placebo is statistically significant at the 0.05 level, no penalty will be assessed to the comparison of the low active arm versus the placebo arm. Otherwise, the low active arm versus the placebo arm will be compared at the 0.025 level.

Missing values for the primary endpoint will be imputed by 2 methods: last observation carried forward and worst observation carried forward. Imputations will be done on the total score level and not on the individual item level. Due to the sample size, no multiple imputation technique is intended.

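### Section 15.3 fixes LOCF and WOCF for missing primary-endpoint scores beside a repeated-measures model that can use incomplete patients as they are; if imputed scores feed it and polyps shrink gradually, the Week 12 difference is mostly understated

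*Protocol*

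**What the plan says.** Section 15.3 compares each AK001 arm with placebo by a "mixed effect repeated measures analysis of variance (ANOVA) model with specific contrast statement for Week 12". It then adds: "Missing values for the primary endpoint will be imputed by 2 methods: last observation carried forward and worst observation carried forward". Imputation is at total-score level, and the section closes the topic with "Due to the sample size, no multiple imputation technique is intended". It does not say whether the imputed scores enter the model, and it gives neither method a sensitivity role. The synopsis describes the same model and does not mention imputation.

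The main population is the Modified Intention-to-Treat Population. The primary analysis is repeated in the Per-Protocol Population, "defined as patients who have a Week 12 visit and valid efficacy measurements" (15.1.3).

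Missing Week 12 scores are to be expected:
- Section 12.1: "All patients who discontinue study treatment should come in for an ET visit as soon as possible".
- Section 12.2 treats stopping treatment early as withdrawing before Day 168. Its reasons for ending participation include "Use of a non-permitted concomitant drug, as defined in" Section 7.1.
- Section 12.3: "Patients who withdraw prematurely from the study will not be replaced".
- Section 9.6.4 schedules post-baseline endoscopy "pre-dose on Days 21 and 49, and on Days 84 and 112 or ET for efficacy analyses". What is available to carry forward is therefore a Week 3, Week 7 or early-termination (ET) score.

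**The concern.** A mixed model fitted by likelihood takes each patient's available visits and, under missing at random, estimates the Week 12 means without filling anything in. Replacing a missing Week 12 score by an earlier one instead assumes that the patient's polyps stopped changing at the last endoscopy (LOCF) or stayed at their worst (WOCF). The sample-size reason in 15.3 argues against multiple imputation only. It gives no ground for carrying scores forward, and the model already avoids the need for either.

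At stake is the estimated effect on the primary endpoint in a trial with 20 to 25 patients per arm. If AK001 acts gradually, scores frozen at an earlier visit pull the AK001 mean toward zero more than the placebo mean. The Per-Protocol repeat cannot settle the matter, because dropping patients without Week 12 data can push the estimate the other way.

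**Working it through.** **The plan's own power figure.** Section 15.7 gives mean changes of -0.3 (SD 1.128, n=20) and -1.9 (SD 2.064, n=25), alpha 0.05, power at least 80%. The standard error is sqrt(1.128²/20 + 2.064²/25) = sqrt(0.0636 + 0.1704) = 0.484, and 1.6/0.484 = 3.31. Two-sided Welch power is 89.7%, so the stated figure is reproduced.

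**Assumptions that the protocol does not supply.** SDs constant over visits; correlation between visits 0.7; dropout share d equal in all arms and random, half after Week 3 and half after Week 7; WOCF does not count Baseline. Gradual onset at Weeks 3/7/12: placebo -0.1/-0.2/-0.3, AK001 -0.7/-1.3/-1.9. The differences are then -0.6, -1.1 and -1.6.

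**LOCF.** Expected difference = (1-d)(-1.6) + (d/2)(-0.6) + (d/2)(-1.1).
- d=5%: -1.52 - 0.015 - 0.0275 = -1.56
- d=10%: -1.44 - 0.03 - 0.055 = -1.525
- d=20%: -1.28 - 0.06 - 0.11 = -1.45

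**WOCF.** A patient lost after Week 7 contributes the larger of two correlated changes. With θ = SD·sqrt(2(1-0.7)) and δ = (Week 3 mean - Week 7 mean)/θ, its mean is m3·Φ(δ) + m7·Φ(-δ) + θ·φ(δ).
- AK001: θ=1.599, mean -0.318. Placebo: θ=0.874, mean 0.201. Difference -0.519, in place of -1.1.
- d=5/10/20%: -1.55, -1.50, and -1.28 - 0.06 - 0.052 = -1.39.

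Simulation gives the same values. The model on observed data stays at -1.60.

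**Power per comparison, two-sided 0.05, gradual onset.**

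| | Full data | 5% | 10% | 20% |
|---|---|---|---|---|
| LOCF, Welch | 89–90% | about 87% | about 86% | about 82% |
| WOCF, Welch | 89–90% | about 86% | about 85% | about 78% |

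Part of this fall is information lost with the patients, which no analysis recovers. A common-variance framework separates the parts at 20%: full data 84%, observed-data model 78%, LOCF 74%, WOCF 69% to 70%. Of LOCF's 10-point fall, 6 points are lost by the observed-data model too, and 4 come from carrying scores forward. These levels are lower than Welch because, with SDs this unequal, the pooled test rejects only about 2.5% of the time under no effect.

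**Where the shift is smaller or reverses.**
- Early onset (differences -1.2/-1.5/-1.6), 20%: LOCF = -1.28 - 0.12 - 0.15 = -1.55.
- ET endoscopy midway to the next visit carried (differences -0.85 and -1.35), gradual onset, 20%: -1.28 - 0.085 - 0.135 = -1.50.
- Waning effect, random dropout: LOCF sizes of 1.61 to 1.68, slightly too large.
- Linear improvement: LOCF enlarges the difference only if placebo dropout exceeds 1.9/0.3 = 6.3 times active dropout.

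**Dropout that is not random (gradual onset).**
- Depends on the last observed score (24% placebo, 18% active): observed-data model -1.60, LOCF -1.43, WOCF -1.41, completers -1.68.
- Depends on the unseen Week 12 score (19% to 26% placebo, 11% to 14% active): observed-data model -1.65 to -1.67, LOCF -1.56, WOCF -1.54 to -1.55, completers -1.70 to -1.74.

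**No true effect.** At 20% equal dropout, or 10% placebo and 25% active, LOCF and WOCF reject in about 5% of Welch comparisons.

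**The case against.** Section 15.3 never says that imputed scores enter the model, and the synopsis gives the model without them. Two unranked methods could be meant as sensitivity analyses, and Section 15 lets the SAP describe data handling in full and modify the plan. This stands as a limit: the harm needs imputed scores in the model, gradual onset and material dropout, and the protocol states none of the three. It does not remove the point, because 15.3 states the imputation rule itself and names no unimputed analysis in the main population. The order of LOCF and WOCF, and what counts as worst, can be left to the SAP.

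The better method also depends on why patients leave. If dropout depends on the unseen Week 12 score, LOCF (-1.56) is nearer to -1.60 than the observed-data model (-1.65 to -1.67), whose error favours the drug. Withdrawal after a prohibited drug makes such dropout plausible. With early onset at 20% dropout, LOCF even has slightly more power than the observed-data model (82% against 79%, common-variance tests). These points stand and are the reason to keep both imputations as sensitivity analyses.

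A reader might infer that carrying scores forward manufactures positive results. The calculations show no raised false-positive rate, and under gradual onset the error mostly runs against AK001. A reader might also infer from the common-variance figures that imputation alone takes the trial well below its 80% target. It does not: much of that gap is the conservative test and lost information. With Welch at 20% dropout, LOCF stays at about 82% and WOCF falls just short at about 78%.

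**Conclusion.** The point holds in conditional form. Section 15.3 prescribes two single imputations that its own model does not need, for a reason that does not support them, and leaves a completer set as the only analysis clearly restricted to observed Week 12 data. Under gradual onset and equal random dropout of 5% to 20%, the Week 12 difference would be understated by 0.04 to 0.15 with LOCF (1.60 - 1.56; 1.60 - 1.45) and by 0.05 to 0.21 with WOCF (1.60 - 1.55; 1.60 - 1.39), with a modest loss of power. The sizes rest on an assumed dropout rate, time course and visit correlation. They shrink with early onset, little dropout or a carried ET score, and can reverse if the effect wanes or placebo dropout is far higher. The documents do not show that the primary result will be biased, only that the stated rule permits it when a better-founded analysis is already at hand. Severity is low to moderate.

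**What to change.** State in 15.3 that the deciding analysis is the mixed repeated-measures model, fitted by restricted maximum likelihood to all observed TPS values in the Modified Intention-to-Treat Population, without imputation, and that LOCF and WOCF are sensitivity analyses.

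The cost is wording only: the model and both imputations are already planned. The downside is reliance on missing at random. In the unseen-score example above, the deciding analysis overstates the benefit by about 0.05 to 0.07, against an understatement of about 0.04 for LOCF. Its estimate is also slightly more variable (SD 0.52 against 0.49 for LOCF at 20% random dropout). Keeping LOCF and WOCF beside it lets the reader see whether the conclusion depends on that assumption.

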15.4 Analysis of Secondary Endpoints

Additional efficacy measures will be analyzed in support of the primary efficacy endpoint results.

In addition to change from Baseline in TPS (Appendix 2 [Section 19.2](#)), absolute values and percentage changes from Baseline will be analyzed separately using the same repeated measures model described above. A responder analysis will also be considered. The response definition and its appropriate analysis methodology will be presented in the SAP. The numbers (percentages) of patients who are responders and time to first response for each active treatment group will be compared separately with the placebo group, if feasible.

Examination of the treatment effect over time for TPS (Appendix 2 [Section 19.2](#)), UPSIT (Appendix 4 [Section 19.4](#)), and patient-reported symptoms of sinusitis (SNOT-22) (Appendix 5 [Section 19.5](#)) will be examined using an appropriate similar repeated measures ANOVA. The stratification factor, presence or absence of asthma, may be included in the model. The details of the analytical methods will be presented in the SAP.

Size of polyps as evaluated by Lund-Mackay score (Appendix 3 [Section 19.3](#)) at selected Investigator sites by CT scan (CT scans are optional and will only be done at Investigator sites at which appropriate and timely regulatory approval or authorization can be granted); PNIF; UPSIT (Appendix 4 [Section 19.4](#)); and patient-reported SNOT-22 (Appendix 5 [Section 19.5](#)), VAS (Appendix 6 [Section 19.6](#)), clinical symptoms improvement scale³ (Appendix 6 [Section 19.6](#)), and SF-36 (Appendix 7 [Section 19.7](#)) scores for each active treatment group will be compared separately with the placebo group using a repeated measure ANOVA with contrast statements for comparison at Week 12 as well as other time points in the study.

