3.2 Secondary Objectives

The secondary objectives are:

1. To evaluate the effect of 2 different dose levels of AK001 in combination with an INS versus the INS alone on changes from Baseline to Week 12 after the start of treatment in:
 - a) Size of polyps as evaluated by Lund-Mackay score (Appendix 3 [Section 19.3](#)) at selected Investigator sites by computed tomography (CT) scan
 - b) Nasal airway patency as evaluated by peak nasal inspiratory flow (PNIF)
 - c) Ability to smell by the University of Pennsylvania Smell Identification Test™ (UPSIT) (Appendix 4 [Section 19.4](#))
 - d) Patient-reported symptoms of sinusitis (Sino-nasal Outcome Test-22 [SNOT-22] [Appendix 5 [Section 19.5](#)] and Visual Analogue Scales [VASs] [Appendix 6 [Section 19.6](#)])
 - e) Clinical symptoms improvement scale³ (Appendix 6 [Section 19.6](#))
 - f) Quality of life (36-Item Short Form Health Survey [SF-36] Appendix 7 [Section 19.7](#))
2. To evaluate the time to first response in TPS (Appendix 2 [Section 19.2](#))
3. To evaluate the change in TPS (Appendix 2 [Section 19.2](#)), UPSIT (Appendix 4 [Section 19.4](#)), and patient-reported symptoms of sinusitis (Appendix 4 [Section 19.6](#)) over time
4. To evaluate the safety and tolerability of 2 different dose levels of AK001 in combination with an INS during 7 weeks of study drug in patients with moderate to severe nasal polyps and whose symptoms are resistant to INSs

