9.6.5 Computed Tomography Scan

At selected Investigator sites, CT scans will be performed at Days -3 and 84 or ET to assess size of nasal polyps based on Lund-Mackay score (Appendix 3 [Section 19.3](#)). The CT scans are optional and will only be done at Investigator sites at which appropriate and timely regulatory approval or authorization can be granted.

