15 STATISTICAL METHODS AND CONSIDERATIONS

This section outlines the nature and rationale for the statistical methods to be used for the analysis of the data from the study. Baseline will be defined as the last measurement before the patient is randomized. All data will be included in data listings. A separate Statistical Analysis Plan (SAP), which must be documented as completed prior to unblinding the study, will describe data handling and statistical techniques in full detail, except missing PK data handling and PK analysis methods will be described in the PK report. The SAP will contain any modifications to the analysis plan described below in this section.

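### Section 15.4 compares scores on seven secondary measures with no change variable or Baseline term, although secondary objective 1 is change from Baseline, and it plans CT contrasts at visits that have no scan

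*Protocol*

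**What the plan says.** Secondary objective 1 (Section 3.2, repeated in the synopsis) is to evaluate each dose with the INS "versus the INS alone on changes from Baseline to Week 12 after the start of treatment in" seven measures: Lund-Mackay score, PNIF, UPSIT, SNOT-22, VAS, the clinical symptoms improvement scale and SF-36.

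The last paragraph of Section 15.4 gives the analysis for these same measures: "scores for each active treatment group will be compared separately with the placebo group using a repeated measure ANOVA with contrast statements". The contrasts cover Week 12 and also other visits. The statistics part of the synopsis says the same in nearly the same words. Neither place names change from Baseline, a Baseline covariate, or Baseline as a level of the response.

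Elsewhere the variable is named. Section 15.3 has each dose "compared separately with the placebo group for change from Baseline in TPS by using a mixed effect repeated measures analysis of variance (ANOVA) model". For TPS, Section 15.4 adds to change from Baseline that "absolute values and percentage changes from Baseline will be analyzed separately using the same repeated measures model described above". Section 15 defines the reference value: "Baseline will be defined as the last measurement before the patient is randomized".

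On imaging, Section 9.6.5 says that at selected sites "CT scans will be performed at Days -3 and 84 or ET". Table 1 and its footnote on CT agree.

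**The concern.** The objective and the analysis paragraph are about the same seven measures but do not name the same variable. Someone who programs Section 15.4 literally would model the visit values. With 20 placebo and 25 active patients in each comparison, the arms will often differ somewhat at Baseline by chance. A model without a Baseline term lets part of that difference into the estimated effect and makes no use of the Baseline measurement.

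For Lund-Mackay there is a second problem that needs no assumption. Contrasts at visits other than Week 12 are planned for a measure with one scan before treatment and one after.

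At stake are the precision and clarity of the secondary results. An unstated variable also leaves room to choose later among visit values, change scores and adjusted results.

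**Working it through.** **The plan's own figure.** The only power statement (Section 15.7) concerns TPS: means -0.3 and -1.9, SDs 1.128 and 2.064, n = 20 and 25, at least 80% power at alpha 0.05. The standard error is sqrt(1.128²/20 + 2.064²/25) = 0.484. A Welch test with 38.5 df has 89.7% power at two-sided 0.05 and 83.1% at two-sided 0.025, so the statement holds. It does not bear on the secondary measures, for which the protocol gives no SD, correlation or power.

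**Chance Baseline difference.** In units of the measure's SD, the standard error of the difference between arms is sqrt(1/20 + 1/25) = sqrt(0.05 + 0.04) = 0.30. The 95% range is ±1.96 × 0.30 = ±0.59 SD. About 32% of comparisons, P(|Z| > 1), start at least 0.30 SD apart. CT is done only at selected sites, so fewer patients contribute. If half were scanned (an assumption), the standard error would be sqrt(1/10 + 1/12.5) = 0.42 SD.

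**How much carries through, and precision.** Let rho be the correlation between Baseline and Week 12, with equal SDs at both times. Rho is assumed, because the protocol gives none. Relative to a visit-value contrast, the variance is:
- visit value: 1
- unadjusted change from Baseline: 2(1 - rho)
- Baseline-adjusted: 1 - rho²

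A Baseline difference of +0.30 SD shifts the visit-value contrast by rho × 0.30 and the unadjusted change contrast by -(1 - rho) × 0.30. Baseline adjustment removes it.

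| | rho 0.3 | rho 0.5 | rho 0.7 |
|---|---|---|---|
| Variance, unadjusted change | 1.40 | 1.00 | 0.60 |
| Variance, Baseline-adjusted | 0.91 | 0.75 | 0.51 |
| Visit value ÷ adjusted, 1/(1 - rho²) | 1.10 | 1.33 | 1.96 |
| Shift, visit value (SD) | +0.09 | +0.15 | +0.21 |
| Shift, unadjusted change (SD) | -0.21 | -0.15 | -0.09 |

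**In terms of power.** Suppose the visit-value comparison had 80% power. Power under another method with relative variance v is about Φ(2.802/√v - 1.960), where 2.802 = 1.960 + 0.842. The Baseline-adjusted model then has 83.6%, 89.9% and 97.5% at rho 0.3, 0.5 and 0.7. Unadjusted change has 65.8%, 80% and 95.1%.

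**CT.** The scheduled scans are Day -3 and Day 84 (or early termination). The number of scheduled post-Baseline scans other than Week 12 is zero, so a contrast at another visit has no scheduled data.

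**The case against.** The paragraph never calls the scores raw or absolute; the noun simply closes a list of instruments. Where the protocol wants unadjusted values, as for TPS, it says absolute. It also drops the word change where change is plainly meant: the paragraph of Section 15.4 on effects over time omits it, although secondary objective 3 asks for change. On this view the objectives supply the variable, Section 15 supplies the model, and the SAP supplies the rest, since Section 15 defers full detail to it. Baseline could be a response level in the model. Even the primary model names no Baseline covariate, and these analyses only support the primary result.

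Much of this stands. A reader might infer that the protocol specifies a raw-score analysis; it does not, and that reading comes from silence. A reader might infer a biased drug effect. Randomization rules that out: differences in Week 12 means and in mean changes have the same expectation, so a visit-value contrast still estimates the effect that the objective asks about. Nor does a Baseline difference enter in full, since only about rho times it does. Nor is precision always lost: against unadjusted change, visit values are equal at rho 0.5 and better below it.

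Deferral to the SAP does not dispose of the point. The paragraph states an analysis which, if followed literally, omits both the objective's variable and the Baseline information. For CT it lists contrasts that the schedule cannot supply. A Baseline response level would give the CT model repeated values, but still no post-Baseline visit other than Week 12.

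**Conclusion.** The point holds as a mismatch of wording with a real but moderate cost. Section 15.4 and the synopsis should name change from Baseline for these seven measures, and the Lund-Mackay contrasts at other visits should go.

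If visit values are compared as written, the cost relative to a Baseline-adjusted model is a variance 1.10 to 1.96 times as large over assumed correlations of 0.3 to 0.7, plus exposure to chance imbalance with a standard error of 0.30 SD (larger for CT). These figures assume equal SDs at Baseline and Week 12 and ignore the one degree of freedom spent on the Baseline slope. They measure the gain from adjustment. They do not measure the difference between visit values and unadjusted change, which can go either way.

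The documents do not support saying that the secondary estimates would be biased or that the objective would go unanswered. The primary analysis and the sample size are untouched.

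**What to change.** Amend the last paragraph of Section 15.4 and its synopsis counterpart:
- State that change from Baseline in PNIF, UPSIT, SNOT-22, VAS, the clinical symptoms improvement scale and SF-36 is analysed in the repeated measures model, with that measure's own Baseline value as covariate and contrasts at Week 12 and the other scheduled visits. With the Baseline covariate in the model, the treatment contrast is the same whether the response is change or visit value, so this matches the objective and gains the precision.
- State that Lund-Mackay is analysed by ANCOVA of the Day 84 score on the Day -3 score, with no contrasts at other visits.

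The cost is wording only. Baseline measurements for all seven are already scheduled, on Day -3 for CT and pre-dose on Day 0 for the others. The change should be made before unblinding.
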